Title: Evaluate the Efficacy of Two Advanced Skin Treatment Regimens in Treating Incontinence-associated Dermatitis: Cluster Randomization Study

Study protocol

Study design

An open-label, cluster randomized, three-group, prospective study will be adopted. Cluster randomization will be used to allocate the selected wards to the experimental or control group for ease of operation (Hemming, Eldridge, Forbes, Weijer, amp; Taljaard, 2017), avoiding confusion on the treatment regimens and cross-contamination of subjects (Sedgwick, 2012). The randomized code for the nursing units will be generated using www.randomizer.org as Treatment 1 or Treatment 2 or Control. Blinding is not possible as the treatment products cannot be “masked”. A purposive sampling on inpatients with IAD will be recruited into the study upon consent. The inclusion and exclusion criteria are as listed in K1 amp; K2. The participants will automatically follow the randomization code selected (implied either control or treatment arm) by the nursing unit he is being admitted.

Study materials

Control

The control regimen for IAD is the current standard of care implemented by the organizations participating in the study. The control regime are combination of treatment - varied practices currently for the treatment of IAD – including the use of potassium permanganate, barrier cream or zinc oxide with skin wipes or soap and water for cleaning

Treatment products

The recommended treatment for IAD should include a structured skin care regimen containing a skin cleanser and a skin protectant. The chemical components recommended as protectants should contain either zinc-based, petrolatum-based, dimethicone-based, or an acrylic polymer. The four preselected products for review are: (1) Conveen easi cleanse and Coloplast Conveen critic barrier (2) 3M No rinse cleanser and 3M Caviton No string Barrier Film (3) 3M No rinse cleaner and 3M Caviton Advanced Skin Protectant(4) Smith and Nephew Moisturizing cleanser and Secura EP cream 30%

Study process

Screening/Recruitment

1. When a potential candidate is identified, the research team members will be activated.
2. Eligible participants from the cluster randomized nursing units will be screened. If they meet the inclusion/exclusion criteria, the PI / co-I will be approached the participants face-to-face.

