3. The study information will be explained to them at their individual bedside cubicles or a quiet corner of the nursing unit for semi-ambulant participants. Time will be given for consideration to the study. All questions asked will be answered. Upon verbal agreement, the consent will be taken using the appropriate ICFs attached.
4. The nurse-in-charge/doctor-in-charge of the patient will be notified of the participant's agreement to the study.

Study day process

5. Arrangement will be made with the nurse-in-charge to synchronize the daily skin assessments with the study assessment to avoid unnecessary exposure.
6. An initial baseline assessment (Day 0) will be conduct on the participant's buttocks, posterior aspect of thigh and perineal region. The subject will be placed on a lateral comfortable position.
7. Observations made will include the amount and extent of denudement, exudate level, redness, signs of infection and the skin condition.
8. A baseline photo will be taken prior treatment.
9. Concealed treatment codes placed in a sealed opaque envelope will be used for randomizing the cluster. Each nursing units will be asked to draw the sealed envelope. With the sealed envelopes contained numbers 1 to 3 where 1 = Standard of care (control), 2 = Treatment regimen 1, 3 = Treatment regime 2. Each draw will determine the allotted treatment for the study site to adopt.
10. The treatment products will be issued to the nurse for application.
11. The treatment regimens will be applied as per manufacturer's recommendation.
12. Patients will be followed up three times a week for a maximum of 21 days, or until the IAD has healed or discharged from the study site.
13. Each review (including baseline assessment), photos will be taken to document the extent of the IAD over the buttocks and/or thighs and/ or perineal region.
14. All assessments will be made using IADS-D and GLOBIAD tool. Permissions to use the assessment tool has been given.
15. On Day 3, 5 and 7, an assessment will be made to the skin appearance if the IAD has not resolved.
16. Patients on treatment regimens will be identified using visual cue - different flower icons. Patients on control regimens will be treated as per hospital policy on data management
17. All collected data will be entered into the CRF.
18. Upon completion of the data collection, the data will be transcribed into EXCEL and validated independently by two different assigned persons.

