19. The validated data in EXCEL will be imported into SPSS and R for data analysis on a later date.

Data collection

Baseline parameters and other outcome measures that will be collected include the pain scores, classification of IAD and healing rates, episodes of incontinence, deterioration to PI or development of other adverse events (Kon et al., 2017) will be collected based on the case record form. Subsequently, 4 more assessments will be made on the participants on the progress of the IAD following treatment(s)/control regimens.

Data Analysis plan

All data will be entered into a Microsoft Office Excel 2013 and independently verified for accuracy of the transcription. The data will then be imported into Statistical Package for the Social Sciences (SPSS) IBM Version 24 and R for analysis and coding. Descriptive analysis including means and standard deviations or medians and interquartile ranges for the numerical variables and frequencies for categorical variables will be used to describe the study sample characteristics. ANOVA will be used to analyse for group differences. The measure of effect (risk difference or mean difference) and a confidence interval or measure of variation will be examined. The intra-cluster correlation coefficient (ICC) will be examined with an ICC of 0.10 used as the acceptable determine for cluster independence during observations (Thomson 2012). Multivariate regression will be used to evaluate the effect of treatment regimens, adjusting for risk factors. A significance level of 0.05 will be used.

We will measure skin characteristics by an independent wound nurse clinician to determine if the photographs reflected any change in skin, size of redness, skin infection or other changes during the follow-up of days 1, 3, 5 and 7 after application of the product. Photographs will be examined to detect any signs of improvement or deterioration in skin condition – redness, maceration of skin and skin erosion (Van de Bussche et al., 2018). A copy of the photograph assessment form is attached. The outcome measures include the pain scores, assessment scores for IAD and healing rates, episodes of incontinence, deterioration to PI or development of other adverse events (Kon et al., 2017).

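### The reason given for not blinding, that the products cannot be masked, does not by itself rule out masking the independent reader of the photographs, and the plan's text does not provide for it

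*Combined protocol and SAP*

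**What the plan says.** The Study design section describes an open-label, three-group trial randomised by nursing unit. It gives one reason for the absence of blinding, "Blinding is not possible as the treatment products cannot be" masked, and makes no distinction between roles. On allocation it says "The participants will automatically follow the randomization code selected" by the admitting unit, so ward determines arm. Study day process, item 16, adds a bedside marker: "Patients on treatment regimens will be identified using visual cue - different flower icons".

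Photographs are taken before treatment (item 8) and at each review (item 13). The Data Analysis plan then assigns their reading to someone outside the bedside process: "We will measure skin characteristics by an independent wound nurse clinician to determine if the photographs reflected any change in skin". It describes the task as "Photographs will be examined to detect any signs of improvement or deterioration in skin condition", covering redness, maceration and erosion, and places the readings "during the follow-up of days 1, 3, 5 and 7 after application of the product". It also says "A copy of the photograph assessment form is attached"; that form was not among the material available here.

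**The concern.** A product that looks different cannot be disguised from the nurse who applies it or the patient who receives it. A person who sees only photographs is in a different position and can often be kept unaware of the arm. The plan names such a person but extends the general statement on blinding to everyone, so a site following it has no instruction to protect this reading.

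Whether redness or erosion has improved is a matter of judgement. A reader who knows the ward, or sees an icon, can work out the regimen, and any expectation about the newer products could then favour one arm. Analysis cannot remove this afterwards, and a reader who has seen the arm for a set of images cannot later be masked for them.

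**Working it through.** No arithmetic applies: the documents give no figure for reader error or bias. The check sets the relevant sections side by side.

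1. **Scope of the reason for no blinding (Study design).** The reason is the appearance of the products. It covers those who apply, receive or see them. It reaches a photo reader only as far as product, packaging, icons or labels show in the image or its file.
2. **Meaning of the reader's independence (Data Analysis plan).** The term is not defined. A clinician can be independent of the ward team and still know which ward, and so which arm, an image came from.
3. **Other wording that might supply masking.** Item 9 conceals treatment codes in envelopes, but this concerns the draw that allocates wards. Item 18 has two people validate independently, but this concerns data transcription. Neither bears on reading photographs.
4. **Image handling (items 8, 13 and 16; Data Analysis plan).** Nothing states how images are labelled, whether ward or regimen is removed, or whether icons are kept out of frame.
5. **Consequence of the cluster design (Study design).** All patients on a ward share its arm. Ward identity is therefore equivalent to arm identity, and stripping only the regimen from a file would not mask the reader.
6. **Days to be read.** The Data Analysis plan reads days 1, 3, 5 and 7, which agrees in number with the four further assessments under Data collection. Item 15 lists only days 3, 5 and 7. Whether a day 1 image exists is therefore unsettled. Baseline is not named among the read days, but judging change needs a reference, and item 8 provides a pre-treatment photograph.
7. **Place of the reading in the results.** The outcome list in the Data Analysis plan covers pain, IAD assessment scores, healing, incontinence episodes, deterioration to PI and adverse events. Photo-read skin change is not listed separately, and no outcome is named as primary.

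**The case against.** - **The attached form may already deal with this.** It is a natural place for reader instructions and image labelling. This stands: what is shown is that the available text is silent. A reader might infer that the wound nurse is unmasked, but the documents do not say so.
- **The stated reason may partly extend to photographs.** Readings follow product application, and control practices include potassium permanganate and zinc oxide. The text does not say whether skin is cleaned before a photograph. Where residue or staining shows, coding the file will not hide the arm. This also stands. It limits what masking can achieve, but gives no reason to leave ward and regimen visible as well.
- **The icons may never appear in an image.** Item 16 says they identify patients, not where they are placed, and the photographs are of buttocks, thighs and perineum. A reader might infer that icons unmask the images; the documents support only an open risk. The ward route to the arm does not depend on icons.
- **The main results may come from the bedside.** Item 14 has all assessments made with IADS-D and GLOBIAD, without saying by whom. If scores and healing come from there, masking the photo reader leaves them exposed. This stands and limits the benefit.
- **The trial is openly declared open-label.** That answers a complaint about open care, which is not made here. Open care and masked outcome reading are compatible.

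**Conclusion.** The point holds in a limited form. The plan's reason for not blinding does not by itself prevent masking the photo reader, and the available text provides neither masking nor image coding. This leaves an avoidable risk of detection bias in a subjective between-group comparison. It should be addressed before reading begins.

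No size can be put on the bias. The conclusion assumes that the attached form does not already mask the reader and that image files could carry ward or regimen information; the documents settle neither. Importance also depends on how much the results rest on the photo reading, which is unclear without a named primary outcome.

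Two stronger inferences are not supported. One is that masking this reader would protect the trial's outcomes generally: pain scores and bedside IADS-D and GLOBIAD scores would be untouched. The other is that masked reading must run through the whole follow-up, because "Patients will be followed up three times a week for a maximum of 21 days" and photographs are due at each review. The Data Analysis plan schedules reading only to day 7, and extending it would add reader work beyond the gap identified here.

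**What to change.** Amend Study design and the Data Analysis plan to say that care is open-label but the photo reader is masked to arm and ward. Then:

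- File the photographs already planned under random codes, with ward and regimen removed. Keep icons and packaging out of frame, or crop them.
- Present each patient's baseline and follow-up images together so that change can be judged, and randomise the order of patients across wards and arms. Shuffling single images would defeat a reading of change.
- Reconcile the read days in the Data Analysis plan (1, 3, 5 and 7) with item 15 (3, 5 and 7), and use the masked reading for the between-group comparison of photo-read skin change on the agreed days.
- State who scores IADS-D and GLOBIAD, and report those scores as unmasked unless that assessor is masked.
- Have the reader record a guess of arm, to show how far masking held.

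If the attached form already masks the reader, it is enough on masking to correct the general statement in Study design to match.

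The cost is some file handling, using photographs already planned and a reader already named, with no extra patient procedure. The downside is that masking may be incomplete where residue or staining is visible.

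### The independent photograph reading is specified only to Day 7, although reviews with photographs may run to Day 21, so later healing or deterioration would rest on unblinded study assessments alone

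*Combined protocol and SAP*

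**What the plan says.** Study day process, item 12, sets the follow-up: "Patients will be followed up three times a week for a maximum of 21 days, or until the IAD has healed or discharged". Item 13 ties photography to that schedule: "Each review (including baseline assessment), photos will be taken to document the extent of the IAD".

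The Data Analysis plan then describes the independent reading: "We will measure skin characteristics by an independent wound nurse clinician to determine if the photographs reflected any change in skin". The days it names are "during the follow-up of days 1, 3, 5 and 7 after application of the product". The next sentence is more general: "Photographs will be examined to detect any signs of improvement or deterioration in skin condition". It gives neither days nor a reader. The paragraph also refers to an attached photograph assessment form, which is not part of the text available here.

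Two other places suggest a one-week schedule. Item 15 says: "On Day 3, 5 and 7, an assessment will be made to the skin appearance if the IAD has not resolved". The Data collection section, after describing baseline, says that "4 more assessments will be made on the participants on the progress of the IAD".

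The Study design section makes the trial open label because the products cannot be disguised. Healing rates and deterioration to pressure injury are among the listed outcomes.

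**The concern.** The wound nurse clinician is the only assessor whom the plan calls independent. In an open-label comparison of skin products, whether redness or erosion has cleared is partly a matter of judgement, and a reading made away from the bedside is a useful check on that judgement. As specified, the check is confined to the first week of a follow-up that may last three.

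Take two patients whose dermatitis heals on Day 5 and on Day 12. The first has an outcome that the independent reader is assigned to see. The second has photographs at every review, but no independent reading of the one on which healing is declared. The same holds for a patient whose skin erodes on Day 10. Patients still under review after Day 7 are by definition the slower ones. If the regimens differ mainly in how many slow cases finally heal, the independent reading as specified cannot show it. If the study assessments do show such a difference, no independent reading is specified to support it.

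**Working it through.** The plan states no figure for this point, so there is none to reproduce. The check has two parts.

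**1. The schedules side by side**

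- Items 12 and 13: 3 reviews a week × 3 weeks = up to 9 reviews after baseline, each with photographs. Follow-up ends earlier at healing or discharge.
- Data Analysis plan, independent reading: Days 1, 3, 5 and 7, which is 4 time points, the last on Day 7.
- Item 15, skin appearance if unresolved: Days 3, 5 and 7, which is 3 time points without Day 1.
- Data collection: 4 assessments after baseline. This agrees with Days 1, 3, 5 and 7 but not with 9 reviews.

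For a patient followed for the full period, weeks 2 and 3 hold about 6 of the 9 reviews, or 21 − 7 = 14 of 21 days (67%), with no independent reading specified. This is the maximum window, not the share of patients or outcomes affected.

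**2. How many healings could fall after Day 7**

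The documents give no time to healing or discharge, so the medians below are assumptions. Let healing occur at a constant rate with median m days.

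*No discharge.* Share of healings by Day 21 that fall after Day 7 = (2^(−7/m) − 2^(−21/m)) / (1 − 2^(−21/m)).

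- m = 5: (0.379 − 0.054) / 0.946 = 34%
- m = 7: (0.500 − 0.125) / 0.875 = 43%
- m = 14: (0.707 − 0.354) / 0.646 = 55%

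*Discharge at an independent constant rate, assumed median 7 days.* Put k = 1/m + 1/7. The proportion of exits that are healings is constant over time and cancels, so the share among observed healings = (2^(−7k) − 2^(−21k)) / (1 − 2^(−21k)).

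- m = 5: 7k = 2.4 and 21k = 7.2, so (0.189 − 0.007) / 0.993 = 18%
- m = 7: 7k = 2 and 21k = 6, so (0.250 − 0.016) / 0.984 = 24%
- m = 14: 7k = 1.5 and 21k = 4.5, so (0.354 − 0.044) / 0.956 = 32%

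Across these assumptions the share runs from 18% to 55%. Faster healing or earlier discharge would make it smaller.

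**The case against.** Several stronger readings are tempting, and the documents do not support them.

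- **A reader might infer that photographs after Day 7 are never read.** The text does not say so. The general sentence on examining photographs has no day limit, and the attached form, which may list reading days, cannot be seen here. What stands is narrower: the visible text assigns the independent reader no photograph after Day 7.
- **A reader might infer that late outcomes rest on ward staff.** Item 5 distinguishes the ward's routine daily skin checks from the study assessment, and no item says that ward staff make the latter. Only the lack of blinding is established.
- **A reader might infer that a masked reading is lost after Day 7.** The reader is called independent, but nothing says that the reader is unaware of allocation. The protection forgone is independence, of unstated strength.
- **A reader might take 67% as the size of the problem.** Patients leave at healing or discharge, and these are inpatients. If nearly all have healed or gone home by Day 7, the gap is small.

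The strongest objection is that Day 7 may be the intended end of outcome assessment, since item 15 and the four planned assessments both fit it. On that view the real defect is an unreconciled schedule, and the photograph reading is only one symptom. This largely stands, and the remedy has to deal with it. It does not remove the point: the plan nowhere limits the analysis of healing or deterioration to Day 7, and it keeps patients and photographs to Day 21.

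It is also fair that photograph reading is not named as the primary outcome. Item 14 bases the assessments on IADS-D and GLOBIAD scores.

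**Conclusion.** The concern holds as a gap in what is specified. The only assessor described as independent has reading days that end at Day 7, while reviews with photographs may continue to Day 21. Under the visible text, healing or deterioration in between would be supported by unblinded study assessments alone. This weakens verification of late outcomes; it does not invalidate the trial.

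The size cannot be determined from the documents. The illustrative range of 18% to 55% rests on constant healing rates with assumed medians of 5 to 14 days, with either no discharge or discharge at an assumed median of 7 days. It shows that the gap could be material, not that it is. The gap affects only patients who are neither healed nor discharged by Day 7. The correction is worth making because the photographs, the reader and the form are already planned.

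**What to change.** Amend the photograph paragraph of the Data Analysis plan so that the same clinician, using the same form, also reads each patient's last available photograph. That is the one from the review at which healing is declared, the last review before discharge, or Day 21. The clinician judges it as healed, improved or deteriorated against the baseline photograph. Keep the Day 7 reading for patients still under review then; patients who heal or are discharged earlier will have no Day 7 photograph.

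In the same amendment, reconcile the reading days with items 12, 13 and 15 and with the count of four assessments in Data collection. State up to which day healing and deterioration are analysed.

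The cost is at most one extra photograph reading for each patient whose last review is not on Day 1, 3, 5 or 7. That can include some patients who leave before Day 7 as well as those followed beyond it. No treatment, review or photograph is added.

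### Episodes of incontinence are listed as an outcome, and their use as a baseline covariate is possible but not secured

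*Combined protocol and SAP*

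**What the plan says.** Incontinence episodes appear twice in the combined protocol and SAP. The closing sentence of the Data Analysis plan places them among the outcomes: "The outcome measures include the pain scores, assessment scores for IAD and healing rates, episodes of incontinence, deterioration to PI". The Data collection section has a single list that does not separate baseline items from outcome items: "Baseline parameters and other outcome measures that will be collected include the pain scores, classification of IAD and healing rates, episodes of incontinence".

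The analysis has two parts. The first is "ANOVA will be used to analyse for group differences", with no covariate or ward term. The second is "Multivariate regression will be used to evaluate the effect of treatment regimens, adjusting for risk factors", with no risk factor named. The test level is given by "A significance level of 0.05 will be used". Clustering enters only through a threshold: "ICC of 0.10 used as the acceptable determine for cluster independence during observations".

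Under Study design, "An open-label, cluster randomized, three-group, prospective study will be adopted", and "The participants will automatically follow the randomization code selected (implied either control or treatment arm) by the nursing unit he is being admitted". Under Study day process, step 9 has each unit draw an envelope, and no stratification or matching of wards is described. Step 12 ends follow-up at healing, at discharge or at 21 days. The number of wards and their size are not given.

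**The concern.** The regimens under Treatment products are a skin cleanser and a skin protectant. They act on the skin. The documents do not say that they leave continence unchanged, but that is the natural premise, and nothing in the documents suggests otherwise. Episodes of incontinence are the continuing insult that the regimens are meant to withstand.

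Two things follow from calling them an outcome. First, a difference between arms is open to being read as a regimen result when it only describes the wards. Second, it leaves unclear whether the same variable will serve as a covariate for healing, PI and pain, where it matters most. Patients take the arm of their ward, so any difference between wards in how incontinent their patients are becomes a difference between arms.

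**Working it through.** The plan gives no sample size, number of wards, healing rate or incontinence distribution, so there is no figure to reproduce. The text settles what role incontinence has. The arithmetic below only illustrates size, and its inputs are assumptions unless stated otherwise.

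**1. Role in the text.**
- Outcome: explicit, in the Data Analysis plan.
- Baseline value: implied by the opening words of the Data collection list. The Day 0 steps (Study day process, steps 6 to 8) mention only skin observations and a photo.
- Covariate: neither named nor excluded in the regression; absent from the ANOVA.

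**2. Effect of an imbalance on Day 7 healing, with no regimen effect.** Assume 60% of infrequently incontinent patients are healed by Day 7 and that frequent incontinence halves the healing hazard. Healing in frequently incontinent patients is then 1 − √(1 − 0.60) = 1 − √0.40 = 0.368.

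| Frequent in arm | Calculation | Healed |
|---|---|---|
| 60% | 0.4 × 0.60 + 0.6 × 0.368 | 46.1% |
| 40% | 0.6 × 0.60 + 0.4 × 0.368 | 50.7% |
| 80% | 0.2 × 0.60 + 0.8 × 0.368 | 41.4% |
| 20% | 0.8 × 0.60 + 0.2 × 0.368 | 55.4% |

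The false gap is 4.6 points for 60% against 40%, and 13.9 points for 80% against 20%.

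**3. How likely such imbalances are by chance.** With k wards per arm, m patients per ward and ward ICC ρ for incontinence, the SD of the difference between two arms in mean incontinence, in patient-SD units, is √(2(ρ + (1 − ρ)/m)/k). At ρ = 0.10 and m = 20 this is √(0.29/k). If half of all patients are frequently incontinent, the SD of that yes/no variable is √(0.5 × 0.5) = 0.5. A 60% against 40% split is then 0.2/0.5 = 0.4 SD, and an 80% against 20% split is 0.6/0.5 = 1.2 SD. By the normal approximation, for one pair of arms:

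| Wards per arm | SD of difference | P(over 0.3 SD) | P(over 0.4 SD) | P(over 1.2 SD) |
|---|---|---|---|---|
| 1 | 0.54 | 58% | 46% | 2.6% |
| 2 | 0.38 | 43% | 29% | 0.2% |
| 4 | 0.27 | 27% | 14% | below 0.1% |
| 8 | 0.19 | 12% | 4% | below 0.1% |

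Across ρ from 0.05 to 0.20 and m of 10 or 20, the SD runs from 0.16 (8 wards per arm) to 0.75 (1 ward per arm).

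**4. Testing incontinence itself as an outcome.** At ρ = 0.10 and m = 20 the design effect is 1 + 19 × 0.10 = 2.9. For a three-group patient-level ANOVA at 0.05 that ignores wards, the large-sample chance of a false difference is P(χ² on 2 df > 5.99/2.9) = exp(−5.99/5.8) = 0.36.

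**5. Carry-over to the other outcomes.** A simulation with 3,000 runs per setting (m = 20; 1, 2 or 4 wards per arm; no regimen effect; ward differences arising only through incontinence) gave these type I error rates at 0.05:

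| ρ | Correlation of incontinence with outcome | Unadjusted ANOVA |
|---|---|---|
| 0.10 | 0.3 | 0.07 to 0.09 |
| 0.10 | 0.5 | 0.13 to 0.14 |
| 0.30 | 0.3 | 0.13 to 0.15 |
| 0.30 | 0.5 | 0.28 to 0.30 |

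With baseline incontinence as a covariate, the rate was 0.045 to 0.058 in every setting.

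**6. Why follow-up totals will not serve.** Follow-up stops at healing. At the same daily rate r, a patient healed at Day 7 contributes 7r episodes and one unhealed at Day 21 contributes 21r. That is a threefold difference with no difference in continence. The plan does not say whether totals or rates will be used.

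**The case against.** A reader might infer that the plan keeps incontinence out of the baseline data and out of the adjustment. The documents do not support that. The Data collection list mixes baseline and outcome items, and incontinence is an obvious candidate for the regression's unnamed risk factors. Recording a variable during follow-up and adjusting for its Day 0 value is ordinary practice, so an outcome label does not by itself rule out use as a covariate.

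Nor does the plan say that a difference in episodes would be reported as a regimen effect. It names no primary outcome and does not say which listed items will be tested.

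The numbers also have limits. Every input to the healing illustration is assumed. In the simulation, incontinence was the only source of ward differences, so adjusting for it was bound to restore the error rate. Steps 4 and 5 therefore show in large part the cost of ignoring wards, which a covariate alone does not repair.

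All of this stands. What remains is that outcome is the only role the text assigns to incontinence in so many words, the ANOVA is unadjusted on any reading, and the choice of risk factors stays open until the data have been seen.

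**Conclusion.** The point holds as a misassigned role with an unsecured remedy. A driver of IAD that the regimens would not be expected to change is listed as an outcome. Its use as a covariate is possible but not committed to.

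The harm shown is chance imbalance between arms when wards are few. A reader might infer a systematic bias, but allocation of wards is random, and the documents do not establish selective recruitment. Nor should about 14 points be read as the expected distortion: it needs an 80% against 20% split, which under the assumptions above is uncommon even with one ward per arm. About 5 points, from a 60% against 40% split, is a more ordinary case if there are only one or two wards per arm, and becomes unlikely with eight. Both figures rest on 60% healing by Day 7 in infrequently incontinent patients and a halved healing hazard in the rest. The number of wards, on which the seriousness depends, is not given.

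**What to change.** - In the Data Analysis plan, remove episodes of incontinence from the outcome measures.
- In Data collection, split the list into baseline items and outcome items, and put incontinence under baseline.
- In the regression sentence, name the baseline (Day 0) value of incontinence episodes as a covariate, in a model that also accounts for ward. Base the treatment comparisons on that model and not on the unadjusted ANOVA.
- Report episodes after Day 0 by arm only as a description of exposure. Do not use the follow-up total as an outcome or a covariate, because its length depends on healing.

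The cost is mainly wording. One check is needed: the sponsor must confirm that the case record form captures a Day 0 value over a defined counting window, since the Day 0 steps under Study day process mention only skin observations and a photo. If the form does not, one baseline item has to be added.
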